- (i) **Screening & Baseline Period:** Once the subject has been established as having the appropriate pre-treatment history, she/he will be asked to complete a review of the informed consent. If the subject agrees to participate in the study, the subject will then complete a screening visit. The study coordinator will complete a headache history questionnaire for the subject. If the subject is recommended for continuation in the study after the screening visit and tentatively approved by a principal investigator, she/he will start a daily headache diary and continue to make entries for twenty-eight consecutive days. Subjects will be given Scion email accounts to be used for submitting headache diary entries. Sites will assist subjects with syncing their Scion email accounts with their smartphones or tablets, and will ensure that subjects can competently take a photo of the ediary form, upload and send according to procedure. If the subject does not complete at least 25 of 28 daily headache diary entries during the baseline period, she or he will be withdrawn and will not proceed to randomization.
- (ii) **Clinic Training Visit:** After enrollment, the completion of one month of daily headache diary entries, and reconfirmation by the relevant investigator of the subject's participation in the study, the subject will come to the clinic for an appointment(s) for training on the use of the CVS device. During the clinic visit, the subject will complete a quality of life (QOL) assessment. The assessment will consist of the HIT-6, BAI, BDI-II and Pittsburgh Sleep Quality Assessment questionnaires. The BAI and BDI-II scores will be tallied with the following outcomes:
 - a. Subjects who score 20 or higher on the BDI-II or answer affirmative to questions 9 on the BDI-form will not proceed to randomization and will be withdrawn from the study.
 - b. Subjects who score 16 or higher on the Beck Anxiety Index will not proceed to randomization and will be withdrawn from the study.

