Less likely:

- Nausea/vomiting

- Headache
- Coughing

All of these side effects are expected to resolve once use of the device is stopped.

7) Study Endpoints

- **Primary Efficacy Endpoint for the Study**

For the twice-per-day active-treatment subjects: During the third month of the first treatment period, their average total number of monthly migraine headache days will be lower than their comparable averages derived from the pre-treatment baseline period. Also, this reduction in migraine headache days will exceed that observed in the twice-per-day placebo group.

- **Secondary Endpoints:**

- The normalized percent-reduction in migraine headache days (during the third treatment month relative to the pre-treatment baseline) in the BID active-treatment subjects will be compared to that of the BID placebo-treatment subjects. Groups will be compared on the basis of percent-change (continuous variable) as well as the “50% responder rates” (discrete variable).
- The reduction in acute (prescribed) medication taken (during the third treatment month relative to the pre-treatment baseline) in the BID active-treatment subjects will be compared to that of the BID placebo-treatment subjects.
- The reduction in subject-perceived headache pain scores (during the third treatment month relative to the pre-treatment baseline) in the BID active-treatment subjects will be compared to that of the BID placebo-treatment subjects.
- To assess whether active treatment results in improved quality of life (related to the reduction in migraine), HIT-6 change scores (end of the first treatment period versus baseline) will be compared across BID active-treatment subjects and BID placebo-treatment subjects.
- To assess whether active treatment results in improvements in depression or anxiety, BDI and BAI scores (end of the first treatment period versus baseline) will be compared across BID active-treatment subjects and BID placebo-treatment subjects.
- To assess whether active treatment results in improved sleep quality, Pittsburgh Sleep Quality Assessment change scores (end of the first treatment period versus baseline) will be compared across BID active-treatment subjects and BID placebo-treatment subjects. Correlational analysis will be performed to determine whether a relationship exists between improved sleep and reduced migraine frequency.

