- To assess whether CVS therapy provides durable migraine prevention after therapy has ceased, the number of migraine days, the reduction in subject-perceived headache pain scores, the number of acute (prescribed) medication taken, during each month in the post-Tx observation period will be compared to both baseline and the final treatment month in all 3 treatment groups. The normalized percent-change in monthly headache days and the 50% responder rates (relative to baseline) will also be assessed. Additionally, the QOL measurements (HIT-6, BDI, BAI and Pittsburgh Sleep Quality Assessment scores) at the final visit will be compared to both the baseline and the 6 month scores.
- Measures of body mass index for each subject will be calculated at baseline, after three and six months of treatment and after the post-treatment observation period and compared across the three treatment

arms.

- Measures of depression (Beck Depression Inventory) and anxiety (Beck Anxiety Inventory) for each subject will be calculated at baseline, after three and six months of treatment and after the post-treatment observation period and compared across the three treatment arms.
- To assess whether the reduction in migraine days relates to the number of active CVS treatments performed, correlational analyses will be performed to assess whether the change in the total number of headache days during defined study periods (first treatment period, second treatment period and post-treatment observational period) is a function of the cumulative CVS treatments performed. Additionally, approaches such as the GLIMMIX procedure for generalized linear mixed models will also be performed to determine the probability of a headache on any given day is predicted by the cumulative number of active treatments performed.

As noted above, the baseline period and the first 3-month treatment period will constitute a complete RCT. Those data will be analyzed when the targeted number of subjects (120) complete the first treatment period. Subjects will continue on to the second 3-month treatment period without interruption, as they progress through the study period. For additional clarity, the stated primary endpoint will be evaluated for the baseline period + first 3-month treatment period.

[figure not shown]
8) Statistical Analysis and Study Size

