An experienced, independent and blinded Statistician will analyze and summarize the daily headache diaries for all subjects and evaluate the primary endpoint and observational aims. A blinded reviewer will analyze and summarize the quality of life data.

The primary aim of this trial is to determine if subjects randomized to the twice-daily active group, have a greater reduction in the number of headache days than those assigned to the twice-daily placebo group. For this study, the reduction in headache days (primary endpoint) is calculated as the number of headache days during the baseline month minus the number of headache days during treatment month three. An intent-to-treat methodology will be employed for the primary aim; however, per protocol analyses will also be conducted for comparison. Analysis of the primary endpoint and the secondary headache-related endpoints assessed in the daily diary will be performed for all subjects that complete at least 25 diary entries or more during the relevant 28-day treatment month. Treatment compliance is defined as completion of at least 50% during

each treatment months (for the per protocol evaluation). Subjects with treatment compliance below 50% during any treatment month will be assigned to the intent-to-treat group only. As accurate assessment of some of the secondary endpoints assessed during study period do not depend on daily headache diary compliance, treatment compliance will be the only criteria for inclusion in the per protocol analysis of those secondary outcomes. Statistical significance will be defined with a Type I error of 5% ($\alpha=0.05$). Wilcoxon rank-sum tests (for non-normal data) or a paired student's t-tests (for normal data) will be used to establish whether the reductions in headache days between the baseline and third treatment month in each treatment arm are statistically significant. Mann-Whitney U tests (for non-normal data) or unpaired student's t-tests (for normal data) will be used to determine whether the reduction in migraine headaches in the twice daily active treatment arm subjects is significantly greater than that observed in the twice daily placebo treatment arm subjects. No interim analyses of efficacy are planned.

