The study is powered for the primary aim. Given a sample size of 40 subjects per arm and a standard deviation in the reduction of headache days of $\sigma=3.36$, a mean difference for the reduction in the number of headache days between the twice-daily active arm and the twice daily placebo arm of 2.13 days will be detectable at the 95% significance level ($\alpha=0.05$) with 80% power. The figure below shows the sensitivity of the detectable differences relative to the value of the standard deviation and the sample size.

The study is intentionally overpowered for the primary endpoint (based on the mean reduction of 2.73 headache days in the first RCT), however, a sample size of 40 subjects per arm should allow for sufficient power to assess the majority of secondary endpoints at

the end of the sixth treatment month and at the end of the post-treatment observation period given the expected dropout rate of 5 subjects per group during each 3 month period. Notably, while the 50% responder rate (a secondary outcome) will be evaluated as a discrete variable, it is unlikely to yield statistical significance due to insufficient sampling. Therefore, the similar measure of percent-change in migraine days will also be compared as a continuous variable across groups.

An analysis will be conducted to determine if blinding was successful using descriptive statistics.

9) Quality Assurance Monitor

A quality assurance monitor will be used to audit study sites. Following written procedures, the monitor will verify that the clinical trial is conducted and data are generated, documented and reported in compliance with the protocol, GCP and applicable regulatory requirements. Investigational site(s) will provide direct access to all trial related sites, source data/documents and reports for the purpose of monitoring and auditing by the sponsor and inspection by regulatory authorities.

10) Procedures for adverse events:

- **Documentation and assessment**
 - Following the informed consent process, clinical study subjects will be routinely questioned about adverse events at study visits and telephone contacts by the clinical research sites. All adverse events, regardless of treatment group, or suspected causal relationship to the investigational device, will be recorded in the subjects' case report forms in their study binder.

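### The one BDI-II/BAI score taken before treatment both decides entry and serves as baseline, so comparing final-visit scores with it within the groups tends to show a rise with no true change

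*Combined protocol and SAP*

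**What the plan says.** **Entry gate.** Section 4, item (ii), has the quality-of-life questionnaires completed at the clinic training visit, after the 28-day baseline diary. The BDI-II and BAI are scored there. A BDI-II of 20 or more, or an affirmative item 9, stops randomisation, and for the BAI: "Subjects who score 16 or higher on the Beck Anxiety Index will not proceed to randomization and will be withdrawn from the study". The Treatment Day 1 (Visit 2) form prints the same cut-offs beneath the recorded scores.

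**Baseline.** The Schedule of Visits and Procedures shows no BDI-II or BAI before Visit 2 and none after it until the end of week 16. The gated score is therefore the only possible baseline. By the bands in the Definitions, every randomised subject starts in the minimal or mild range: BDI-II 0-19 and BAI 0-15, on scales that run to 63.

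**Use.** In section 7 one secondary endpoint reads "To assess whether active treatment results in improvements in depression or anxiety, BDI and BAI scores", compared between BID active and BID placebo at the end of the first treatment period. The durability item adds: "QOL measurements (HIT-6, BDI, BAI and Pittsburgh Sleep Quality Assessment scores) at the final visit will be compared to both the baseline", and also with the 6-month scores. From week 16 all groups receive the active device, and in the last three months none is treated. Section 8 names no baseline adjustment for these scales and does not mention regression to the mean.

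**The concern.** A single BDI-II or BAI score is part stable level and part visit-to-visit variation. Removing everyone above a cut-off on one administration removes some people whose score happened to be high that day, and keeps others whose score happened to be low. If that same administration is the baseline, the retained group's mean is too low as a reference, and the next measurement rises on average with nothing having changed.

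The comparison exposed to this is final visit versus baseline. A rise there could be read as a late mood effect of the device, and would sit awkwardly beside section 6, which cites the absence of negative mood changes in the first trial as safety evidence. No concurrent placebo group exists at that point to show that the rise is a selection effect.

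**Working it through.** **1. The plan's own power figure.** Section 8 says "Given a sample size of 40 subjects per arm" and gives SD 3.36, alpha 0.05 and 80% power, with a detectable difference between the "twice-daily active arm and the twice daily placebo arm of 2.13 days". The two-sided two-sample t-test gives 0.634 × 3.36 = 2.13, so the figure reproduces. It concerns headache days. No power figure is given for BDI-II or BAI.

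**2. Number at the final visit.** Section 3 aims for 120 subjects completing period 1, or 40 per arm. Section 8 expects 5 dropouts per group in each 3-month period. Two periods follow: 40 − 5 − 5 = 30 per arm.

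**3. Assumptions.** The documents give no BDI-II or BAI distribution and no retest correlation. Assumed: right-skewed (gamma) pre-gate scores rounded to 0-63, mean/SD of 6/6, 8/7 or 10/8, retest correlation r of 0.7 to 0.9, and no true change. Each gate was simulated separately. The test is also an assumption: section 8 names a paired test only for headache days, so a paired t-test at two-sided 0.05 is used, with 2.5% nominal in the worsening tail.

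**4. Results with no true change, n = 30 per arm.**

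| Scale (kept if) | Pre-gate mean/SD | r | Removed | Drift | SD of change | False worsening |
|---|---|---|---|---|---|---|
| BDI-II (<20) | 6/6 | 0.9 | 4% | +0.1 | 2.7 | 3% |
| BDI-II (<20) | 10/8 | 0.75 | 12% | +0.66 | 5.00 | 8% |
| BDI-II (<20) | 10/8 | 0.7 | 12% | +0.8 | 5.5 | 9% |
| BAI (<16) | 6/6 | 0.9 | 8% | +0.2 | 2.5 | 4% |
| BAI (<16) | 10/8 | 0.75 | 20% | +0.9 | 4.7 | 15% |
| BAI (<16) | 10/8 | 0.7 | 20% | +1.1 | 5.1 | 17% |

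Hand check of the second row: rejection rate ≈ 1 − Φ(t − drift × √n / SD), with t = 2.045 on 29 degrees of freedom. The shift is 0.66 × √30 / 5.00 = 0.72, and 1 − Φ(2.045 − 0.72) ≈ 9%. The simulated 8% is slightly lower because the scores are skewed.

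**5. Is the gate the cause?** In scenarios with pre-gate means of 8-12 and r of 0.6-0.9, taking baseline from an administration not used for the gate, with cut-offs unchanged, reduces the drift to 0.00-0.01 points. With gate and baseline combined, the same scenarios give +0.28 to +1.01 (BDI-II) and +0.37 to +1.40 (BAI).

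**6. Which comparisons are affected?**
- BID active versus BID placebo at the end of period 1: the drift is the same in both arms. Simulated type I error is 0.044-0.051 in the 10 scenarios checked.
- BID versus QD, BID active versus BID placebo at month 6, and scores compared across the three arms: all are between randomised groups, so the drift again cancels.
- Month 3 versus month 6 change scores: the common baseline cancels. Final visit versus 6 months: both scores come after the gate. Simulated drift between two such visits is essentially zero.
- Final visit versus baseline within the groups: affected, as in step 4.

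**The case against.** The strongest reply is that the stated mood endpoint is a randomised comparison and is unbiased, and that only one sentence of section 7 is exposed. That stands. So does the point that the size rests wholly on assumed distributions. Section 2 already excludes unstable mood or anxiety disorder, so the Visit 2 gate may remove few people, and the drift would then be negligible. The drift also runs against the device and cannot create a false improvement.

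A reader might infer more: that with every subject in the minimal or mild range the trial could hardly show a mood benefit. The documents do not support that. The low scores in the simulations come largely from the assumed pre-gate means, and the gate narrows the spread as well as the range. Under the assumptions in step 3, the difference detectable at 40 per arm is 1.6-3.5 points with the gate and 1.9-4.1 without it. As a share of the baseline mean that is 26-57% against 24-53%, which mainly reflects 40 per arm. For follow-up scores 25% or 40% lower, simulated power (BDI-II, 10/8, r = 0.75) is 0.53 gated against 0.49 ungated, and 0.93 against 0.88. The gate does limit the population to which a result applies, but no loss of power is shown.

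A reader might also take an apparent loss of benefit after stopping as an artefact of the gate. That would be read from final visit versus 6 months, which the gate does not materially affect.

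**Conclusion.** The concern holds for one comparison, and it is minor. Final-visit BDI-II and BAI compared with the gated Visit 2 baseline will tend upward with no true change, and the design has no placebo group after week 16 to separate this from a real effect. The direction follows from the design, though a real time trend could mask it. The size does not follow: under the assumptions in step 3 it is about +0.1 to +0.8 points (BDI-II) and +0.2 to +1.1 (BAI), with false worsening in about 3-9% and 4-17% of trials at 30 per arm against 2.5% nominal. Higher pre-gate scores or lower retest correlation would enlarge it, and few exclusions would make it negligible. The between-arm endpoints, the comparisons between later visits and the primary analysis are not materially affected.

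**What to change.** In sections 7 and 8:

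- Base inference on BDI-II and BAI on the randomised BID active versus BID placebo comparison at the end of period 1, adjusted for the Visit 2 score (for example, analysis of covariance).
- Make the durability comparison of final-visit BDI and BAI with baseline descriptive only, and state that it is subject to regression to the mean because the baseline score was also the entry gate.
- Do not add an improvement analysis in subjects with high baseline scores. Selection from below has the opposite artefact: with baseline BDI-II of 14 or more and no true change, the simulated mean falls by about 0.5 to 3.5 points.

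The entry rule is unchanged. The cost is a few sentences. The Visit 2 score is already collected, so no new data are needed. The sponsor gives up only a formal within-group test of final mood scores against baseline.

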The design size contemplates enrolling up to one hundred and twenty (120) subjects who will successfully follow through to completion of their participation in at least the first treatment portion of the study (first 3-month treatment period). The subjects will be randomly assigned to: twice-per-day active, once-per-day active or twice-per-day placebo in a 1:1:1 ratio.

The results of the first migraine RCT did not show evidence of stratification based on gender or clinical site or baseline headache frequency. Envelopes containing

randomization assignments will be grouped in batches of six, each batch containing two of each of the three assignment arms. The batches of envelopes will be randomly shuffled by an agent not involved with the study. A given batch will be completed before the next batch is opened. This procedure results in 20 possible different arrangements, for six subjects, of the ordering of treatment and placebo assignments. The unblinded coordinator will record the subject's designation but will not share the assignment with the subject, principal investigator, or statistician. Each study site will be individually randomized (no central randomization).

The assessment of the primary endpoint will be completed by a blinded, central statistician. The subjects will be told, within the informed consent document, of the existence of a placebo arm. Subjects will be told that the device stimulates the brain stem. Subjects will be told that they will receive at least 3-months of active treatment during the 6-month treatment period. In fact, subjects in the placebo arm in the first 3-month period will be switched to active in the second 3-month period. Subjects will be asked to guess (and provide reasons) about their treatment assignment at the end of the first 3-month treatment period and at the end of the second 3-month treatment period. Subjects will also be asked, after their very first treatment in the clinic, a series of questions designed to assess the quality of blinding (to provide evidence that the placebo device is an effective sham).

4) Study Schedule; Subject Enrollment and Activities

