- (iii) Also, women of childbearing age will complete a urine-based pregnancy test to reconfirm that they are not pregnant. The unblinded coordinator will open, at random, an envelope assigning the subject to one of the three study arms. The clinic period is described below. During the first visit, the subject will complete a training session based on a set training module. The subject will complete a proficiency evaluation and the study coordinator will certify the subject's proficiency in the use of the CVS device. The study coordinator will

complete a visit assessment form. At the end of training, a first usability questionnaire will be completed by the subject.

(iv) **First Treatment Period:** The eighty-four days (3 months) following the pre-treatment baseline period constitute the first treatment period. This is the test period, the results from which will be measured against the pre-treatment baseline period data in assessing the study endpoints. Specifically, data from the last month of the first treatment period will be compared with the one-month-long pre-treatment baseline period. As close as possible (as scheduling permits) to two weeks after the start of treatment, a clinical visit will occur and another visit assessment form will be completed. A second usability questionnaire will be completed. The subject will be asked to bring the CVS device to the clinic to perform a treatment in front of the unblinded study coordinator to reaffirm proficiency in using the device. Any issues related to balance or other safety concerns will promptly be referred to the site principal investigator, who can terminate the subject's further participation in the study if necessary.

(v) **End of First Treatment Period – Start of Second Treatment Period:** At the end of the first treatment period the subject will be asked to return to the clinic and will be asked to complete the QOL questionnaires and a third usability questionnaire. All subjects will receive new SD cards for the second treatment period and the old SD cards will be retained so that treatment compliance logs can be extracted. All subjects will receive active treatment cards with the following assignments (first treatment period -> second treatment period):

- BID placebo -> BID active
- BID active -> BID active
- QD active -> QD active

Subjects will perform a treatment in front of the unblinded coordinator to re- confirm their ability to properly use the device.

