- To assess whether BID active treatment provides therapeutic gains over QD active treatment, the reductions in migraine headaches, the reduction in the number of acute (prescribed) medication taken, the reduction in subject-perceived headache pain scores, the normalized percent-change in monthly headache days, and the 50% responder rates in the BID active-treatment subjects and QD active-treatment subjects during the following periods will be compared: the first treatment month, the third treatment month, the sixth treatment month and the final month of the post-treatment period. Additionally, change scores for the QOL measures (HIT-6, BDI, BAI and the Pittsburgh Sleep Quality Assessment) at the end of the first and second treatment periods and the post-treatment observation period will also be assessed. The response kinetics for each of these parameters will be evaluated by comparing time courses for each of the three treatment arms. All change scores will be calculated relative to baseline measures.
- To assess whether six months of active treatment provides improved levels of migraine prevention relative to three months of active treatment, comparisons of the reductions in migraine headache days, the reduction in the number of acute (prescribed) medication taken, the reduction in subject-perceived headache pain scores, the normalized percent-change in monthly headache days, and the 50% responder rates during the third treatment month and the sixth treatment month (relative to baseline) for the QD active and the BID active groups will be performed. Change scores for the QOL measures (HIT-6, BDI, BAI and the Pittsburgh Sleep Quality Assessment) for the QD active and the BID active groups at the end of the first and second treatment periods (relative to baseline) will also be compared. Additionally, these measures will also be compared between the BID active and BID placebo groups during the sixth treatment month. All change scores will be calculated relative to baseline measures.

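### The month-3 versus month-6 comparison in the active arms has no concurrent control; the randomised month-6 contrast already planned should be named as the analysis of six versus three months for BID

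*Combined protocol and SAP*

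**What the plan says.** Section 7 (Secondary Endpoints) has one bullet on treatment duration. Its purpose is "To assess whether six months of active treatment provides improved levels of migraine prevention relative to three months of active treatment". Comparisons of several diary measures "during the third treatment month and the sixth treatment month (relative to baseline) for the QD active and the BID active groups will be performed". Quality-of-life change scores are handled in the same way. The bullet then adds: "Additionally, these measures will also be compared between the BID active and BID placebo groups during the sixth treatment month".

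Section 4, item (v), gives the second-period assignments. One of them is "BID placebo -> BID active"; the two active arms continue unchanged. At treatment month 6 the arm labelled BID placebo has therefore had three months of BID active treatment, and the BID active arm six.

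Section 3 allocates subjects to "twice-per-day active, once-per-day active or twice-per-day placebo in a 1:1:1 ratio", so there is no once-daily placebo arm.

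Section 8 states that the diary analyses are "performed for all subjects that complete at least 25 diary entries or more during the relevant 28-day treatment month". It names within-arm tests for baseline versus month 3 only, gives no test for month 3 versus month 6, and has no rule for missing months. It sizes the trial for later time points "given the expected dropout rate of 5 subjects per group during each 3 month period".

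**The concern.** A within-arm difference between month 3 and month 6 mixes the effect of three more months of treatment with everything else that changes over that time: natural course, expectation, the new treatment cards issued at the switch, and who is still contributing a diary. Neither active arm has a control for time in that comparison.

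The 25-entry rule is applied month by month, so the month-3 and month-6 sets need not be the same people. If subjects who do poorly leave in between, the month-6 mean rises although nobody has changed.

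At stake is a claim that longer treatment works better, drawn from a comparison that cannot separate duration from time. Between BID active and placebo-to-BID-active at month 6, changes over time common to both arms cancel. The plan contains that contrast but does not say that it answers the question, and its label invites a reader to take it for a sham comparison.

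**Working it through.** **Inputs from the documents**
- 40 subjects per arm, SD 3.36 days for the reduction, alpha 0.05, 80% power, detectable difference 2.13 days; 5 dropouts per group per three-month period (Section 8).
- The 40 per arm are subjects who complete the first treatment period (Section 3), so about 40 − 5 = 35 remain at month 6.
- First trial, change from baseline to month 3: −3.6 days active, −0.9 ± 0.7 days placebo (Background).

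**Assumptions, not in the documents**
- SD of the month-3 to month-6 change: 2.0, 2.5 or 3.36 days.
- Drift between the two months unrelated to longer treatment: 0.25, 0.5 or 0.9 day. The top value borrows the first trial's placebo change over a different interval.
- SD of the month-6 reduction stays at 3.36.

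**Step 1. The plan's own figure.** A two-sample t-test, two-sided 0.05, 40 per arm and SD 3.36 gives a detectable difference of 2.13 days at 80% power. It reproduces.

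**Step 2. Drift in a paired test, 35 subjects, no benefit of longer treatment.** Noncentrality = drift / (SD of change / √35). For example, 0.9 / (2.0/√35) = 2.66, which gives a probability of significance of 73%.

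| SD of change | 0.25 day | 0.5 day | 0.9 day |
|---|---|---|---|
| 2.0 | 11% | 30% | 73% |
| 2.5 | 9% | 21% | 54% |
| 3.36 | 7% | 14% | 34% |

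The nominal rate is 5%.

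**Step 3. Loss of non-responders, each month analysed on its own available subjects.** If the month-3 mean is 3.6 days in 40 subjects and the 5 who leave had no reduction, the mean among those who stay is 40 × 3.6 / 35 = 4.11 days. The apparent gain is 0.51 day with no change in anyone.

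A simulation that removes the 5 worst month-3 responders of 40 gives an apparent gain of 0.38 to 0.61 day when the month-3 and month-6 reductions correlate at 0.5 to 0.8. If only subjects with both months are used, the sign reverses: −0.38 to −0.15 day.

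**Step 4. The randomised contrast at month 6, 35 per arm, SD 3.36.**
- Detectable difference at 80% power: 2.28 days (2.13 at 40 per arm, 2.47 at 30).
- Power for an assumed extra gain: 0.5 day 9%, 1.0 day 23%, 1.5 days 45%, 2.0 days 69%.
- A 1-day gain would need about 178 per arm (normal approximation).
- Standard error 3.36 × √(2/35) = 0.80 day, so a 95% interval extends about 2.0 × 0.80 = 1.6 days either side.
- If one arm loses its 5 worst responders and the other a random 5, the bias is 0.39 to 0.61 day at correlation 0.5 to 0.8.

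**The case against.** The strongest reply is that the remedy is already in the plan: the same bullet says that "these measures will also be compared between the BID active and BID placebo groups during the sixth treatment month", and Section 7 also compares time courses across all three arms. A reader might infer that the plan ranks the within-arm comparison as the lead test, or leaves the randomised one out. The documents support neither: there is no stated hierarchy, and the order is only that of sentences. Aim 2 itself speaks only of extending treatment and claims no superiority. What stands is that the plan does not say which comparison answers the question.

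A reader might also infer that a 0.9-day drift is to be expected. The documents do not support that. The figure runs from baseline to month 3, where regression to the mean and the onset of placebo response fall, and nothing suggests a second fall of that size. At 0.25 day the excess over 5% is small.

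Nor do the two harms add up. The dropout gain needs separate available-case sets, while the drift percentages need a paired test, which the plan does not name. In an unpaired comparison of 40 with 35, the standard error is 3.36 × √(1/40 + 1/35) = 0.78 day, and a 0.51-day artefact would be significant in only about 10% of trials.

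Finally, the randomised contrast is not a pure or decisive test of duration. It is open to unequal dropout. The delayed arm moves from unpowered earpieces to active waveforms, after all subjects were told to expect at least three months of active treatment, so a noticed switch could raise expectation in that arm alone. Its detectable 2.28 days is close to the first trial's whole active-versus-placebo effect of 2.73 days. All of this stands. It limits how the contrast may be read, but does not make the uncontrolled comparison an adequate substitute.

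**Conclusion.** The point holds as a matter of which comparison carries the inference. The within-arm comparison cannot separate longer treatment from time, nor, with month-by-month analysis sets, from changing membership.

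The size depends on assumptions. If a paired test were used, the false-positive rate would run from slightly above nominal at a small drift to 34–73% at the extreme one. The dropout artefact is about half a day, in an available-case comparison only. Drift sizes, correlations, the SD of change and the month-6 SD are not given in the documents.

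The randomised contrast should carry the BID question as an estimate with its interval. With 23% power for a 1-day gain, a non-significant result would say little, and must not be read as showing that three months is as good as six. This is a secondary endpoint; the primary analysis is unaffected.

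**What to change.** In Sections 7 and 8:

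1. Name BID active versus placebo-to-BID-active at treatment month 6, as change from baseline and by randomised arm, as the analysis of six versus three months for BID.
2. Relabel the arm as placebo-to-active wherever second-period results are compared.
3. Report the estimate with a 95% confidence interval, and state that non-significance is not evidence of equivalence.
4. Report month-3 to month-6 changes within the QD and BID active arms descriptively, in subjects with both months, labelled uncontrolled and without a significance claim.
5. State how missing month-6 diaries are handled in the randomised contrast, since randomisation does not protect it from unequal dropout.

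The cost is wording only: no new data, visits or subjects. The price is precision, because the two-arm contrast has low power for modest gains. It also stays exposed to unequal dropout and to expectation if the switch is noticed; the second-period treatment guess can help describe the latter. QD has no delayed-start comparator, so its duration question gets no controlled answer, and the report should say so.
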